#### **C4. Scoring algorithm for Patient Global Assessment**

The Patient Global Assessment is a 10 cm visual analog scale with 0 being very well and 10 very poor. The score on this instrument is taken directly from the mark made by the patient on the VAS.

#### **Appendix D. Analytical Windows**

The last measurement for the endpoint of interest taken prior to or on the first dose of IP in this study, unless stated otherwise, will be defined as a baseline visit and the analysis visit name will be 'Baseline'. For any visit up to Day 1 pre-dose which is not a baseline visit, the analysis visit will be 'Pre-analysis'.

Since the actual visit for a subject may not exactly coincide with their scheduled visit date, to allow for variations in scheduling, the following visit windows will be used to assign evaluations to a most appropriate nominal visit for analysis and summarization. Furthermore, there will be no gaps between visit windows in order to include as many data points as possible for summarization.

If more than one actual visit (including the unscheduled visits) falls within the same defined window, the visit closest to the target day with non-missing data will be considered for analysis. If two actual visit dates are at the same distance from the target day, the latest visit with non-missing data will be considered for analysis.

The rules above for selecting a visit from multiple ones within the same visit window are not applicable to retest values of lab data. If the lab measurement is a retest, the retest value will be used.

**Efficacy assessment (tender/swollen joint count, hSLEDAI, BILAG, [REDACTED]  
[REDACTED], PGA VAS, PGA 4-Point Verbal Rating Scale, CLASI), weight,  
and laboratory assessment (anti-dsDNA, C3 and C4 complement, chemistry,  
urinalysis)**

Study Visit	Target Day	Study Day
Baseline	1	Last evaluation prior to or on Study Day 1
Week 4	29	2 - 42
Week 8	57	43 - 70
Week 12	85	71 - 98
Week 16	113	99 - 126
Week 20	141	127 - 154
Week 24	169	155 - 182
Week 28	197	183 - 210

Week 32	225	211 - 238
Week 36	253	239 - 266
Week 40	281	267 - 294
Week 44	309	295 - 322
Week 48	337	323 - 350
Week 52	365	351 - 394

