2.2.2.2 Human Exposure

The observed efavaleukin alfa human exposures from single ascending doses of efavaleukin alfa ranging from [REDACTED] in the first in human (FIH) study 20140324 in healthy subjects and all available **pharmacokinetic** (PK) data up to [REDACTED] from 3 phase 1b studies (20170103 in subjects with SLE; 20170149 in subjects with RA; and 20160283 in subjects with cGvHD) were used to predict efavaleukin alfa exposures at the selected dose levels for the current study in subjects with SLE ([Table 2-1](#)). The

geometric mean C_{max} and AUC_{inf} increase approximately dose proportionally over the dose range of [REDACTED]. The estimated terminal phase half-life ranges from about 10.6 to 30.4 hours. Given the estimated half-life, minor accumulation of efavaleukin alfa is expected at the selected dose levels with Q2W dosing regimens in patients with SLE.

Table 2-1. Steady-state Median (IQR) of Efavaleukin Alfa Pharmacokinetic Parameter Prediction Following Q2W Subcutaneous Doses in Subjects with SLE

Dose	AUC_{ss} (day•ng/mL)	C_{max} (ng/mL)
[REDACTED]	11.75 (8.18 - 16.20)	9.30 (7.55 - 11.47)
Q2W	22.88 (15.87 - 32.27)	18.91 (14.96 - 23.16)
Q2W	43.10 (29.92 - 60.31)	34.84 (27.81 - 43.10)

AUC_{ss} = area under the serum concentration curve at steady state; C_{max} = maximum observed concentration; IQR = interquartile range; Q2W = every 2 weeks; SLE = systemic lupus erythematosus

A detailed description of the chemistry, pharmacology, and safety of efavaleukin alfa is provided in the Investigator's Brochure.

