8.1.2 Treatment Period

Visits will occur per the Schedules of Activities (Table 1-2 and Table 1-3). The date of the first dose of investigational product is defined as day 1. All subsequent doses and study visits will be scheduled based on the day 1 date. The investigational product is to

be administered following the completion of all other study required procedures for that visit.

If a subject discontinues investigational product prior to week 52, the subject will be encouraged to maintain the planned scheduled assessments through week 52 ([Table 1-3](#)). If the subject discontinues the study completely prior to week 52, the subject should complete an early termination (ET) visit (ie, week 52 visit procedures) which must be scheduled to allow for at least 6 weeks for safety data collection after last dose of investigational product.

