  - At the 'all-subjects-week-24 IA', if this likelihood is sufficiently high with at least one efavaleukin alfa dose level, this IA will trigger an administrative success signal. This would not alter the ongoing or planned activities of this phase 2b study, but downstream planning for subsequent trials (e.g., a phase 3 study) may commence.
- **Based on the Data Monitoring Committee's recommendation following review of the results from the 3rd IA and subsequent decision by the Data Access Plan Team, the study was terminated due to futility and further enrollment in the study was stopped. Previously enrolled subjects were discontinued from IP and terminated the study after being followed for an additional 6 weeks following last dose of IP. The remaining planned IAs, including the 4th to the last IA ('all-subjects-week-24-IA') were not conducted.**

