### 8.3 Handling of Missing and Incomplete Data

Subjects may have missing specific data points for a variety of reasons. In general, data may be missing due to a subject's early withdrawal from study, a missed visit, or non-evaluability of a specific clinical or laboratory measurement at its planned clinical visit.

**Additionally, as the study was terminated before the planned completion, subjects may have missed clinical visits including not completing the week 52 visit. For efficacy and PRO outcomes, subjects who terminated early due to sponsor decision will be excluded from analyses of data from visits for which they did not have the opportunity to participate in by the date of study termination decision being communicated to sites, i.e. April 5, 2023. Efficacy data collected after this date will be censored and excluded from analyses for that particular visit.** Unless specified, no imputation will be used. The general procedures outlined below describe what will be done when a data point is missing.

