## 9.5 Efficacy Analyses

Unless stated otherwise, the Full Analysis Set (FAS) will be used for analysis of efficacy endpoints. The efficacy analyses are summarized in [Table 9-1](#), [Table 9-2](#) and [Table 9-3](#).

The SLE efficacy assessment data (BILAG, hSLEDAI, PGA, CLASI, swollen and tender joint counts, and [REDACTED]) will be submitted to an external independent committee comprised of clinicians with expertise in managing and assessing SLE disease and clinical trials for adjudication. The committee will adjudicate the data and determine whether the efficacy assessments are scored correctly and consistently based on the instruments' specifications.

Unless stated otherwise, the analysis of the SLE efficacy assessment data and their derived endpoints (SRI-4, BICLA, LLDAS and BILAG flare index) will be based on the data resulting from the adjudication. Additionally, **to assess the concordance between the investigators and adjudicators, the SRI-4 responses at week 16, 20, 24 and 52 based on the two sources will be cross-tabulated and** the concordance rate will be computed as the frequency of cases where the data based on the investigator's assessment and the data resulting from adjudication agree on classification of a subject as an SRI-4 responder/non-responder. If the concordance rate at week 52 is < 0.95, the primary endpoint may be **summarized** using SRI-4 responses derived based on the investigator-reported data **as a sensitivity analysis**.

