#### **9.7.1 Analyses of Pharmacokinetic Endpoints**

**Amgen Clinical Pharmacology Modeling and Simulation (CPMS) group will conduct PK analysis. Serum concentration data will be summarized by treatment for each PK sampling time point. PK parameters may be summarized if adequately estimated.**

**The descriptive statistics for absolute change from baseline, percentage change from baseline and ratio to baseline will be provided by treatment arms at specified time-points for the endpoints C3, C4, anti-dsDNA antibody and antiphospholipid**

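### Complement and autoantibody samples from the termination visit are tabulated as ordinary study weeks, because the 5 April 2023 cutoff covers only efficacy and PRO data

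*SAP*

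**What the plan says.** **How subjects left.** SAP 3.1 records that, after the third interim analysis, enrolled subjects were taken off IP and "terminated the study after being followed for an additional 6 weeks following last dose of IP". Protocol 8.1.2 requires anyone leaving before week 52 to have an early termination (ET) visit with the week 52 procedures, which "must be scheduled to allow for at least 6 weeks for safety data collection after last dose" of IP. The week 52/ET column of protocol Table 1-3 includes anti-dsDNA, C3 and C4, and antiphospholipid antibodies.

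**What the cutoff covers.** SAP 8.3: "For efficacy and PRO outcomes, subjects who terminated early due to sponsor decision will be excluded" from visits they had no chance to attend by 5 April 2023, the date sites were told. It adds: "Efficacy data collected after this date will be censored and excluded from analyses for that particular visit". SAP 9.5 defines the relevant data as instrument scores: "The SLE efficacy assessment data (BILAG, hSLEDAI, PGA, CLASI, swollen and tender joint counts, and" one redacted item. Appendix D names anti-dsDNA, C3 and C4 as laboratory assessments, apart from the efficacy assessments.

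**What is still summarized.** SAP 9.7.1 keeps descriptive statistics for change against baseline, in absolute and percentage terms. It adds that the "ratio to baseline will be provided by treatment arms at specified time-points for the endpoints C3, C4, anti-dsDNA antibody and antiphospholipid" antibodies.

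**How samples get a week.** Appendix D uses study day only, and "there will be no gaps between visit windows in order to include as many data points as possible for summarization". If several visits fall in one window, the one closest to target is used. C3, C4 and anti-dsDNA have windows from Week 4 to Week 52. Antiphospholipid antibodies have two: Week 24 (days 2 to 266) and Week 52 (days 267 to 378). None of these markers has a follow-up row.

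**A possible limit.** SAP 5.3 and 5.4 define a Treatment Period that can end at the (redacted) date of study early termination. No visible biomarker summary or window refers to it.

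**The concern.** By-visit tables are read as the state of each arm at that week of the dosing schedule. Under the rules above, a Week 24 cell for C3 can hold values from subjects on their dosing schedule beside values from subjects whom the sponsor had taken off IP six weeks before. Nothing in the table would tell them apart.

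The plan is also uneven. The hSLEDAI in SAP Appendix B scores 2 points for low complement and 2 points for increased DNA binding. A termination sample is cut from hSLEDAI as post-cutoff efficacy data, while the same sample enters the C3, C4 and anti-dsDNA tables as a nominal week. With treatment comparisons removed (SAP 10), these descriptive tables are what readers will have on complement and autoantibodies by dose.

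**Working it through.** **Inputs.** Windows from SAP Appendix D. Dosing every 2 weeks from day 1, last planned dose at week 50 (day 351). Termination sample 42 days after the last dose, with 42 to 47 days as an assumed range.

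**1. Reproduce the no-gaps statement.** There are 13 post-baseline windows for C3, C4 and anti-dsDNA. Each target equals 7 × week + 1, and each window opens the day after the previous one closes, so days 2 to 394 are covered. The two antiphospholipid windows cover days 2 to 378. The statement holds.

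**2. Would the 8.3 date catch these samples?** A subject dosed on schedule had a last dose no more than 14 days before 5 April 2023. A sample 42 days after that dose falls at least 42 − 14 = 28 days after the cutoff. It would be removed if the rule applied.

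**3. Map the termination sample** (day = last-dose day + 42).

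| Last dose (day) | Sample (day) | C3, C4, anti-dsDNA | Antiphospholipid |
|---|---|---|---|
| 1 | 43 | Week 8 | Week 24 |
| 57 | 99 | Week 16 | Week 24 |
| 85 | 127 | Week 20 | Week 24 |
| 127 | 169 (on target) | Week 24 | Week 24 |
| 225 | 267 | Week 40 | Week 52 |
| 323 | 365 (on target) | Week 52 | Week 52 |

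For last-dose days 1 to 351 and offsets 42 to 47 there are 351 × 6 = 2106 combinations. A nominal week is given in 2096 (99.5%) for C3, C4 and anti-dsDNA, and in 2001 (95.0%) for antiphospholipid antibodies. The rest fall after day 394 or day 378. These are shares of day combinations, not of subjects.

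**4. Does the closest-to-target rule remove them?**
- C3, C4, anti-dsDNA: for all 26 two-weekly last-dose days, no scheduled draw up to the last dose shares the termination sample's window. The gap is at least 42 days, and the windows from Week 8 to Week 48 are 28 days wide. The exception is a subject dosed through week 50, who has a regular week 52 sample closer to target.
- Antiphospholipid: with last dose on days 169 to 211, a regular week 24 sample exists and wins. With last dose up to day 155, or from day 225 to 323, no scheduled sample taken up to the last dose competes. In the extremes, day 43 stands for Week 24 (169 − 43 = 126 days early) and day 267 stands for Week 52 (365 − 267 = 98 days early).

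A visit between the last dose and termination could also compete, but that sample would itself come after IP was stopped.

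**The case against.** **The half-life.** A reader might infer that these samples must dilute the drug's effect, since protocol 2.2.2.2 says "The estimated terminal phase half-life ranges from about 10.6 to 30.4 hours". The documents do not support that step. Dosing is every 2 weeks and assessments precede the dose, so a routine sample is already 14 × 24 = 336 hours after the last dose: 336/30.4 = 11 to 336/10.6 = 32 half-lives. Half-life therefore does not separate regular from termination samples, and no passage says how long an effect on complement or autoantibodies lasts. The low-dose IL-2 trial in protocol 2.2.1.3 reports SRI-4 of 65.52% versus 36.67% 12 weeks after the last dose, though for another agent and endpoint. Dilution is possible but not shown.

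**SAP 8.3 is not an off-drug rule.** A reader might take it as the SAP already excluding off-drug efficacy data. It is a calendar cutoff framed around the opportunity to attend a visit. Subjects who stop IP for their own reasons are encouraged to keep attending, and their data remain. This stands. It means the remedy should follow the sponsor's termination, not time since last dose, which would change what the tables describe.

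**Window width.** The antiphospholipid windows are wide because the planned post-baseline time points are week 24 and week 52. That is a defensible choice, and narrowing them would break the no-gaps principle.

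**Safety laboratories.** The same mapping affects chemistry and haematology, but SAP 9.6 states that safety data to end of study are used. That is deliberate, and the point does not extend to it.

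**Redaction and weight.** The exploratory endpoints are not shown and the date of study early termination is blacked out, so a rule in hidden text cannot be excluded. These markers are not listed as primary or secondary endpoints, and no test remains.

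None of this supplies a visible rule for the biomarkers.

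**Conclusion.** The point holds on the visible text, for C3, C4, anti-dsDNA and antiphospholipid antibodies only. As written, a termination sample taken about 6 weeks after sponsor-directed discontinuation gets an ordinary week label in nearly all timings. It usually has no regular sample to displace it, except for antiphospholipid antibodies when the last dose fell on days 169 to 211.

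The effect is confined to descriptive biomarker tables. No primary or secondary endpoint and no stopping decision is affected. How many values are involved cannot be computed, because the documents do not say how many subjects were on study, or at what week, when it stopped. The direction and size of any distortion are likewise unknown.

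The conclusion assumes that ET visits were done as the protocol requires, about 42 days after the last dose, and that no redacted text restricts these summaries. It is worth correcting before the tables are run, but it is not critical.

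**What to change.** In SAP 9.7.1, state that for subjects terminated by sponsor decision the by-visit summaries of C3, C4, anti-dsDNA and antiphospholipid antibodies use samples up to 5 April 2023. The Treatment Period of SAP 5.3 and 5.4 is an alternative. The April date is simpler, because it is the one applied to hSLEDAI.

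In Appendix D, add a Post-treatment/ET row for these markers and report the later samples there by arm, with counts. Haematology and vital signs already have a Week 56 row, so the device is familiar. State whether lupus anticoagulant is derived for the new row, since SAP 8.3 limits it to baseline, week 24 and week 52. Leave the windows and the safety laboratory rules as they are.

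The cost is SAP wording and one visit flag, with no new data. The downside is fewer values at the nominal weeks.

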### **Hematology**

Study Visit	Target Day	Study Day
Baseline	1	Last evaluation prior to or on Study Day 1
Week 4	29	2 - 42
Week 8	57	43 - 70
Week 12	85	71 - 98
Week 16	113	99 - 126
Week 20	141	127 - 154
Week 24	169	155 - 182
Week 28	197	183 - 210
Week 32	225	211 - 238
Week 36	253	239 - 266
Week 40	281	267 - 294
Week 44	309	295 - 322
Week 48	337	323 - 350
Week 52	365	351 - 378
Week 56	393	≥ 379

### **Vital sign**

Study Visit	Target Day	Study Day

Baseline	1	Last evaluation prior to or on Study Day 1
Week 2	15	2 - 21
Week 4	29	22 - 35
Week 6	43	36 - 49
Week 8	57	50 - 63
Week 10	71	64 - 77
Week 12	85	78 - 91
Week 14	99	92 - 105
Week 16	113	106 - 119
Week 18	127	120 - 133
Week 20	141	134 - 147
Week 22	155	148 - 161
Week 24	169	162 - 175
Week 26	183	176 - 189
Week 28	197	190 - 203
Week 30	211	204 - 217
Week 32	225	218 - 231
Week 34	239	232 - 245
Week 36	253	246 - 259
Week 38	267	260 - 273
Week 40	281	274 - 287
Week 42	295	288 - 301
Week 44	309	302 - 315
Week 46	323	316 - 329
Week 48	337	330 - 343
Week 50	351	344 - 357

[figure not shown]
Week 52	365	358 - 378
Week 56	393	<math>\geq 379</math>

**Anti-phospholipid antibodies**

Study Visit	Target Day	Study Day
Baseline	1	Last evaluation prior to or on Study Day 1
Week 24	169	2 - 266
Week 52	365	267 - 378

**SF-36v2, PROMIS Fatigue SF 7A, LupusQoL**

Study Visit	Target Day	Study Day
Baseline	1	Last evaluation prior to or on Study Day 1
Week 4	29	2 - 56
Week 12	85	57 - 98
Week 24	169	99 - 210
Week 36	253	211 - 308
Week 52	365	309 - 394

## Appendix E. Handling of Dates, Incomplete Dates and Missing Dates

The reference date for the following rules is the date of first dose efavaleukin alfa.

Start Date		Stop Date						
		Complete: yyyymmdd		Partial: yyyymm		Partial: yyyy		Missing
		< 1 st dose	≥ 1 st dose	< 1 st dose yyyymm	≥ 1 st dose yyyymm	< 1 st dose yyyy	≥ 1 st dose yyyy	
Partial: yyyymm	= 1 st dose yyyymm	2	1	n/a	1	n/a	1	1
	≠ 1 st dose yyyymm		2	2	2	2	2	2
Partial: yyyy	= 1 st dose yyyy	3	1	3	1	n/a	1	1
	≠ 1 st dose yyyy		3		3	3	3	3
Missing		4	1	4	1	4	1	1

1=Impute the date of first dose or the randomization date if not treated; 2=Impute the first of the month;

3=Impute January 1 of the year; 4=Impute January 1 of the stop year

Note: For subjects who were never treated (first dose date is missing), partial start dates will be set to the first day of the partial month or first day of year if month is also missing.

### Imputation Rules for Partial or Missing Stop Dates

Initial imputation

- If the month and year are present, impute the last day of that month.
- If only the year is present, impute December 31 of that year.
- If the stop date is entirely missing, assume the event or medication is ongoing.

If the imputed stop date is before the start date, set stop date to missing.

If the imputed stop date is after the death date, impute as death date.
